6.1 Number of subjects

40 patients will be enrolled in the study.

6.2 Study flow chart

48-hour cardiac monitors will be placed for each subject over the three-day interdialytic interval and in the HD2-HD3 interval of Week 0 and Week 4. An Electrocardiogram (ECG) will also occur in week 0.

6.3 Determination of eligibility

The study team will review records of prevalent Duke patients in the DaVita outpatient dialysis facilities. Patient eligibility will be determined. If routine measurements of serum potassium indicate either at least two measured pre-dialysis serum $[K] \geq 5.5$ mEq/L or one $[K] \geq 6.0$ mEq/L noted over the preceding three months, patients medical record will be reviewed to determine whether the remaining inclusion and exclusion criteria are met. The physician rounding in the dialysis unit will be asked if it is suitable to approach the patient. Eligible patients will be approached for the informed consent process.

6.4. Consent

Patients will be provided the Informed Consent Form and this will be reviewed by the Study Personnel. Patients will be encouraged to take the form home and review with their family if possible

6.5 Baseline period, Week 0

Once a patient has signed the ICF, a 12 lead ECG will be obtained. The long term cardiac monitor will be placed at the end of HD3 prior to Week 0 and removed at the beginning of HD3 of Week 0. Weight, pulse, and blood pressure will be recorded. Medical history and demographic data will be collected. Medications will be recorded. The hemodialysis prescription for target weight and dialysate potassium and calcium will be recorded.

Before each hemodialysis session in Week 0, blood samples will be collected and sent to the clinical laboratory. The Renal Function Panel and magnesium levels will be determined with these samples before the first dialysis session of the week (HD1). Serum pregnancy test will be measured for females of child-bearing potential.

6.6 Randomization

Randomization will occur at any time in Week 0 prior to HD3. This will be done using the REDCap system and will assign patients 1:1 to either continue usual care or to receive patiromer as detailed below.

6.7 Open-label patiromer and dose titration, Weeks 1, Week 2, Week 3, Week 4.

Patients randomized to the patiromer arm will initiate on 8.4 g/day (one pack) given once a day with breakfast or lunch, to start after HD3 at the end of Week 0. The patient is instructed to not take any other medications for three hours before or three hours after patiromer.

The patiromer dose will be titrated based on serum potassium concentrations on HD1 of weeks 1, 2, and 3. Patiromer will be increased by 8.4 g/day if $K \geq 5.5$ meq/L, decreased by 8.4 g/day if $K < 4.5$ mEq/L, and patiromer will be discontinued if $K < 4$ mEq/L.

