Randomization ¹			X													
Initiation of Patiromer ²				X												
Patiromer titration ³					X			X				X		X		
Physical Exam		X														
Vital Signs ⁴ (BP, HR, Height, Weight)		X			X				X			X		X		X
Renal Function Panel		X														
Serum Potassium			X	X	X				X			X	X	X	X	X
Serum Magnesium		X							X			X				X
Serum Pregnancy Test ⁵		X														
Holter Monitor Applied	X															X
Holter Monitor Removed			X													
Previous medication and concomitant medication		X	X	X	X				X			X		X	X	X
Adverse Event Questioning		X	X	X	X				X			X		X	X	X
Dialysis ⁶																
ECG	X	←								→						

1=Randomization can occur at any point after Week 0 HD1 as long as it is completed prior to Week 0, HD3.

2=If randomized to the Patiromer Arm

3=Patiromer will be increased by 8.4 g/day if K \geq 5.1 mEq/L, decreased by 8.4 g/day if K<4.0 mEq/L, and discontinued if K<3.5mEq/L

4= Blood Pressure taken after sitting for 5 minutes; Height only collected at Week 0, HD1

5=Females of child bearing potential

6= Hemodialysis should be performed 3 times per week

BIBLIOGRAPHY

6. System USRD. 2017 USRDS annual data report: Epidemiology of kidney disease in the United States. Bethesda, MD: National Institutes of Health, National Institute of Diabetes and Digestive and Kidney Diseases; 2017.

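### Minor safety gap: the first patiromer dose is not tied to the Week 0 potassium, although at 8.4 g/day both versions of the titration rule give zero below 4.0 mEq/L

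*Combined protocol and SAP*

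**What the plan says.** Section 6.7 sets the start: "Patients randomized to the patiromer arm will initiate on 8.4 g/day (one pack) given once a day with breakfast or lunch", beginning after HD3 of Week 0. In the Section 10 schedule, the only condition on initiation is footnote 2: "2=If randomized to the Patiromer Arm".

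The potassium rule comes later: "The patiromer dose will be titrated based on serum potassium concentrations on HD1 of weeks 1, 2, and 3". Two versions of it are written:

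- Section 6.7, repeated in 6.13 and 6.14: "decreased by 8.4 g/day if $K < 4.5$ mEq/L" and "patiromer will be discontinued if $K < 4$ mEq/L", with an increase at K ≥ 5.5.
- Schedule footnote 3: "decreased by 8.4 g/day if K<4.0 mEq/L, and discontinued if K<3.5mEq/L", with an increase at K ≥ 5.1.

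Section 6.13 acts on the Week 1 HD1 value at HD2 or HD3 of that week. The schedule row "Patiromer titration" appears, as extracted, to be marked at Week 1 HD1 itself.

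Samples exist before the first dose. Section 6.5 says "Before each hemodialysis session in Week 0, blood samples will be collected and sent to the clinical laboratory", with the renal function panel at HD1. The schedule as extracted marks serum potassium at HD2 and HD3.

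Sections 5.2 and 5.3 require two pre-dialysis values ≥ 5.5 or one ≥ 6.0 in the past three months. They set no lower potassium limit.

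**The concern.** Eligibility looks back three months at a quantity the protocol itself describes as episodic. A patient with K < 4.0 in Week 0 would still be handed a potassium binder and would take it until the first titration step. The same result one week later, on drug, would bring the dose to zero.

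Low values matter on the protocol's own account. Section 3.1 reports rising risk of peri-dialytic sudden cardiac arrest on both sides of 5.1 mEq/L. Section 3.5 reports hypokalemia in 5.6% of patients in the 52-week patiromer trial. At stake is a short, avoidable exposure in a small number of patients. The validity of the primary comparison is not in question.

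**Working it through.** **1. What each rule gives at a current dose of 8.4 g/day**

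| Potassium (mEq/L) | 6.7, 6.13, 6.14 | Footnote 3 |
|---|---|---|
| < 3.5 | stop: 0 | stop: 0 |
| 3.5 to < 4.0 | stop: 0 | 8.4 − 8.4 = 0 |
| 4.0 to < 4.5 | 8.4 − 8.4 = 0 | 8.4 |
| 4.5 to < 5.1 | 8.4 | 8.4 |

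The versions agree on zero for every K < 4.0 and differ from 4.0 to 4.4. The agreement is specific to this dose: at 16.8 g/day and K 3.5 to 3.9 the results would be 0 and 8.4.

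**2. How many patients**

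Allocation is 1:1 of 40, so 20 start patiromer. The documents give no rate of K < 4.0 for this population. Section 3.1 gives 9% of measurements below 4.0 in a large dialysis organization. I assume a per-patient rate q from 1% to that 9%.

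- Expected number, 20q: 0.2 at 1%; 1.8 at 9%.
- Chance of at least one, 1 − (1 − q)^20: 0.18 at 1%; 0.85 at 9%.
- Chance of two or more, 1 − (1 − q)^20 − 20q(1 − q)^19: 0.02 at 1%; 0.55 at 9%.

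**3. Exposure before the dose can change**

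I assume a Monday-Wednesday-Friday schedule (Tuesday-Thursday-Saturday gives the same counts) and a first packet on the day of HD3 or the day after.

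- Change at Week 1 HD1: 3 days, 2 to 3 packets, 16.8 to 25.2 g.
- Change at HD2 (6.13): 5 days, 4 to 5 packets, 33.6 to 42.0 g.
- Change at HD3 (6.13): 7 days, 6 to 7 packets, 50.4 to 58.8 g.

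**4. Size of the potassium fall**

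Section 3.4 gives two relevant figures. One is 0.35 mEq/L at week 4 for a 4.2 g twice-daily start (8.4 g/day) in CKD with mild hyperkalemia. The other is 0.4 mEq/L on 4.2 g three times daily (12.6 g/day) in six HD patients, p = 0.08. If either fall carried over in full, K 3.9 would reach 3.9 − 0.35 = 3.55 or 3.9 − 0.40 = 3.50. The hypokalemia limit in Section 3.5 is below 3.5.

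**5. Cost of withholding, in power**

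The plan's own figure comes first. A two-sided two-sample t test with 20 per group, difference 2, SD 2 and alpha 0.05 has noncentrality 2 / (2 × √(2/20)) = 3.16 on 38 df. Power is 86.9%, against the stated 86%.

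If k of 20 patients are never dosed and gain nothing, the difference becomes 2 × (1 − k/20). The SD in that arm rises to √(4 + 4p(1 − p)), with p = k/20.

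| Never dosed | Difference | Power, SD 2 | Power, raised SD |
|---|---|---|---|
| 0 | 2.0 | 86.9% | 86.9% |
| 1 | 1.9 | 83.3% | 82.5% (SD 2.047) |
| 2 | 1.8 | 79.2% | 77.4% |
| 3 | 1.7 | 74.5% | 71.9% |

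**The case against.** **Existing safeguards.** Entry selects for recent hyperkalemia. The treating physician must judge the patient stable. The trial is open label, with Week 0 samples sent to the clinical laboratory. Potassium is measured again about three days after the start, and Section 6.15 requires withdrawal when the investigator thinks that is best for the subject. A fixed start followed by titration is a stated choice in Section 3.4. All this stands, and it keeps the point small. It does not close the gap, because the 6.15 clause removes a subject from the study and says nothing about whether to give a first dose.

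**No demonstrated harm.** This also stands. The 0.35 figure is a week-4 result under titration (mean 18.5 g/day after 4 weeks in mild hyperkalemia), so it probably overstates the effect of 3 to 7 days on one packet. Both source groups began hyperkalemic, so transfer to K < 4.0 is uncertain.

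**The cut-off is a choice.** Under 6.7 alone, the same logic would reach 4.5. That is correct. Below 4.0 is simply the region where both versions agree.

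**Extraction.** The schedule's column headings are broken and the flowchart in Section 2 is not shown. The statement that nothing ties the first dose to potassium covers the readable text only.

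A reader might also infer that the protocol contradicts itself by giving a dose its own rule would stop. It does not: the titration rule is written for patients already on drug.

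**Conclusion.** The gap is real and minor. The readable text starts every patiromer-arm patient on 8.4 g/day whatever the Week 0 potassium, and at that dose both versions of the titration rule give zero for K < 4.0.

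The size rests on an assumed rate of 1% to 9%. The 9% describes measurements across a dialysis organization rather than patients chosen for hyperkalemia, so it is best read as a probable upper end. Two stronger readings should be resisted:

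- **Patients would become hypokalemic.** The documents quantify no such harm, and the falls they report come from longer or higher dosing.
- **At most one patient would be affected.** The documents give no rate that supports this; at 9%, two or more would be affected with probability 0.55.

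The point is worth considering because the samples are already ordered and the remedy is short. It is not a flaw in the primary analysis.

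**What to change.** Add to Section 6.7 and as a schedule footnote:

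> Review the Week 0 HD1 pre-dialysis potassium (HD2 if HD1 is not available) before dispensing. If K < 4.0 mEq/L, withhold the first dose and start 8.4 g/day at the first later HD1 (Weeks 1 to 3) with K ≥ 4.5 mEq/L; then titrate as in 6.7.

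The explicit restart level is needed. Under 6.7 the dose rises only at K ≥ 5.5, so a patient held at zero with later values of 4.5 to 5.4 would otherwise stay at zero, possibly through the Weeks 3 and 4 endpoint window. The level of 4.5 is where 6.7 keeps 8.4 g/day.

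State that patients at 4.0 to 4.4 start by choice. The value 4.0 is the stop threshold in 6.7, and 4 to 5.5 is the lowest-mortality range in one cohort cited in Section 3.1 (another gives 4.6 to 5.3). A cut-off of 4.5 is defensible but would withhold from more patients.

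Follow withheld patients and analyse them as randomised. In the same edit, bring footnote 3 (5.1/4.0/3.5) into line with 6.7, 6.13 and 6.14 (5.5/4.5/4.0). That mismatch is a separate matter and adds no weight here.

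The cost is a few lines of text and no extra sample, assuming the HD1 renal function panel reports potassium. The contrast is slightly diluted: one never-dosed patient of 20 takes power from 86.9% to about 83%. The real loss is probably smaller, since some withheld patients will start later and those low at baseline may have few episodes to prevent.

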High serum potassium contributes to cardiac risk. Maintaining serum potassium homeostasis is critical to create a stable transmembrane potential of about -85 mV, and this permits normal cardiac and skeletal muscle function ⁸. Abrupt changes in serum potassium levels result in deviations in membrane potential that can lead to muscle paralysis and to fatal arrhythmias ⁸. In patients with ESRD, the ability to maintain potassium balance by the kidney is diminished, and therefore acceptable potassium conditions can only be approximated by dietary potassium restriction and clearance with dialysis. In a patient maintained on a conventional, three-times-per-week HD regimen, potassium intake is recommended to be limited to about 60 mEq/day (420 mEq/week). Dialysis removal typically is around 70-100 mEq per treatment (210-300 mEq/week for thrice-weekly schedules)². Assuming that native kidney function accomplishes minimal potassium clearance, to maintain a near-steady potassium concentration potassium elimination through the gastrointestinal tract is essential.

In the general population, the normal range for serum potassium is typically reported between 3.5 and 5.0 mEq/L but in HD patients the ideal serum potassium concentration tends to be higher. In a study of 2,134 HD patients, a pre-dialysis serum potassium level of 5.1 mEq/L was associated with the lowest risk of peri-dialytic sudden cardiac arrest, while potassium levels above and below 5.1 were associated with increasing risk ⁵. Another study examining pre-dialysis serum potassium levels and survival within a cohort of 81,013 hemodialysis patients, potassium concentrations between 4.6-5.3 mEq/L were associated with the lowest incidence of all-cause mortality ⁹ and a survey of 55,183 HD patients in the Dialysis Outcomes and Practice Patterns Study (DOPPS) multinational cohort confirmed that the lowest risk of death was observed among patients with serum potassium levels between 4 and 5.5 mEq/L and a significant increased risk of death and arrhythmia outcomes at potassium values ≥ 5.6 mEq/L ¹⁰. In a study of serum potassium values obtained within a large dialysis organization, approximately 20% of all serum potassium measurements were ≥ 5.5 mEq, and about 12.5% of measurements were ≥ 6.0 , whereas potassium < 4.0 accounted for only 9% of all measurements ⁴.

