3.5 Adverse events with patiromer

In the published clinical trial of patiromer that was the longest duration (52 weeks), hypomagnesemia (7.2%) was the most common treatment-related adverse event, mild to moderate constipation (6.3%) was the most common gastrointestinal adverse event, and hypokalemia (<3.5 mEq/L) occurred in 5.6% of patients ²⁸.

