6.12 Concomitant medications

Except for those listed in the exclusion criteria, all medications (prescription or over-the-counter) initiated prior to enrollment may be continued during the course of the study.

All medications that are continued from the start of the study or that are started during the study (other than the study medication) including prescription or over-the-counter will be documented by the study team.

6.13 Follow-up evaluations Weeks 1, 2

A member of the study team will see the patient at the start of HD1 Week 1. Weight, pulse and blood pressure will be recorded. A pre-dialysis serum potassium lab sample will be collected and sent to the clinical lab. Concomitant medications will be recorded.

With study team visit on HD2 or HD3 of Week 1, the patiromer dose will be titrated based on the pre-dialysis potassium measured at HD1. Patiromer will be increased by 8.4 g/day if $K \geq 5.5$ meq/L, decreased by 8.4 g/day if $K < 4.5$ mEq/L, and patiromer will be discontinued if $K < 4$ mEq/L.

6.14 The assessment period Weeks 3, 4 and 6

A member of the study team will see the patient at the start of HD1 Week 3 and HD1 Week 4. Weight, pulse and blood pressure will be recorded. A pre-dialysis serum potassium lab sample will be collected and sent to the clinical lab to measure potassium. Concomitant medications will be recorded.

With study team visit on HD1 of Week 3, the patiromer dose will be titrated based on the pre-dialysis potassium measured at HD1. Patiromer will be increased by 8.4 g/day if $K \geq 5.5$ meq/L, decreased by 8.4 g/day if $K < 4.5$ mEq/L, and patiromer will be discontinued if $K < 4$ mEq/L.

The long term heart monitor (LTHM; Telepatch #2) will be placed at the end of HD3 Week 3 and removed at the beginning of HD3 of Week 4.

With study team visit on HD1 of Week 6, weight, pulse and blood pressure will be recorded. A pre-dialysis blood sample will be collected and sent to the clinical lab for a renal function panel. Concomitant medications will be recorded.

6.15. Withdrawal of subjects.

A subject may discontinue participation in the study at any time without being obligated to give a reason, although they are free to do so if they wish.

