8.1. Primary analysis

This is a proof-of-concept study, to determine the extent to which administration of patiromer has the potential to change the risk category for ESRD patients who are on conventional HD schedules. In addition, the study

aims to develop and test study procedures and instruments that will be implemented in a large-scale clinical trial.

By nature of the size of the study, the power of the trial will be limited for the primary analysis. The proposed primary endpoint is the between-group differences of the number of episodes, per subject, of serum K \geq 5.5 mEq/L during Weeks 3 and 4. This will be assessed as follows: Six serum samples will be collected and assessed for each patient during the efficacy phase (Weeks 3 and 4). Patients would receive a score of perfect K control (6 of 6 samples in range; Score 1.0), moderate K control (5 of 6 in range; Score 0.83), inconsistent K control (4 of 6 in range; Score 0.67), erratic K control (3 of 6 in range; Score 0.50), poor K control (2 of 6 in range; Score 0.33), very poor K control (1 of 6 in range; Score 0.17), or no K control (0 of 6 in range, Score 0). These scores will then be averaged for the patients in the active treatment group and the control group, and the results will be compared. Using this approach, a sample size of n=20 per group provides 86% power to detect a between-group difference of 2 in mean episodes of hyperkalemia per patient, assuming $\alpha=0.05$ and standard deviation 2.

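### Sections 6.7 and 6.14 tie the low-potassium decrease and stop criteria to HD1 of Weeks 1-3, leaving up to five of the six Week 3-4 potassium results with no stated low-potassium action while patients remain on drug

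*Combined protocol and SAP*

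**What the plan says.** - **Section 6.7, text.** "The patiromer dose will be titrated based on serum potassium concentrations on HD1 of weeks 1, 2, and 3". The next sentence gives an 8.4 g/day increase at K of 5.5 mEq/L or more and an 8.4 g/day decrease below 4.5, "and patiromer will be discontinued if $K < 4$ mEq/L".
- **Section 6.7, heading.** "Open-label patiromer and dose titration, Weeks 1, Week 2, Week 3, Week 4". It names Week 4; the text does not.
- **Section 3.4.** Titration uses pre-dialysis potassium in Weeks 1, 2 and 3, without limiting it to HD1.
- **Section 6.13.** "With study team visit on HD2 or HD3 of Week 1, the patiromer dose will be titrated", using the HD1 result, so the change may come one or two sessions after the sample. The heading covers Weeks 1 and 2, but the body describes only Week 1.
- **Section 6.14.** "With study team visit on HD1 of Week 3, the patiromer dose will be titrated based on the pre-dialysis potassium measured at HD1". HD1 of Week 4 has a visit and a potassium draw but no dose step.
- **Section 8.1.** "Six serum samples will be collected and assessed for each patient during the efficacy phase (Weeks 3 and 4").
- **Schedule of Assessments.** The titration row has four marks. Its footnote 3 gives thresholds of 5.1, 4.0 and 3.5 mEq/L, which differ from those in 6.7, and has no HD1 limit.
- **Section 6.15.** Item 3 requires withdrawal for confirmed K above 7 mEq/L in Weeks 2 to 7. Item 2 requires withdrawal when the Investigator judges it best for the subject. No item names a low potassium value.

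**The concern.** The stop criterion is written as one limb of the titration rule, so it ends when titration ends. Under 6.7 and 6.14 a value that requires stopping drug on HD1 of Week 3 requires nothing stated at the next session, even though the result is already being obtained for the primary endpoint.

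The gap falls late in treatment. Starting at 8.4 g/day, three permitted increases give 16.8, 25.2 and 33.6 g/day, the last on the HD1 Week 3 value, and no maximum is stated. Section 6.9 holds the dialysis prescription fixed, so the protocol offers no other stated adjustment for a low value. High potassium has a withdrawal rule independent of titration visits; low potassium does not.

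The protocol itself treats low values as a risk. Section 3.5 reports from a 52-week trial that "hypokalemia (<3.5 mEq/L) occurred in 5.6% of patients", and section 3.1 cites a cohort in which "potassium levels above and below 5.1 were associated with increasing risk". The primary endpoint counts only values of 5.5 mEq/L or more, so a low value does not register there as an unfavourable result.

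**Working it through.** The plan gives no figure for this point. Its one computed figure, 86% power in 8.1, is not involved.

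**Step 1. List the samples.** Section 8.1 gives six samples in Weeks 3 and 4 under thrice-weekly dialysis: W3-HD1, W3-HD2, W3-HD3, W4-HD1, W4-HD2, W4-HD3.

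**Step 2. Remove those that carry a dose decision, under each reading.**

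| Governing text | Week 3-4 decision points | Results with no stated low-potassium action |
|---|---|---|
| 6.7 text and 6.14 | W3-HD1 | 6 - 1 = 5 |
| Schedule, if the four marks are HD1 of Weeks 1-4 | W3-HD1, W4-HD1 | 6 - 2 = 4 |
| 3.4 (every pre-dialysis value in Weeks 1-3) | W3-HD1, W3-HD2, W3-HD3 | 6 - 3 = 3 |

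The Schedule's column alignment is broken in the text version, so placing its fourth mark at W4-HD1 is an assumption.

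**Step 3. Time on drug.** On a Monday/Wednesday/Friday calendar, HD1 of Week 3 to HD3 of Week 4 is 7 + 4 = 11 days. Dosing starts after HD3 of Week 0 and lasts 4 weeks, so patients not already stopped remain on drug over this span.

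**Step 4. Order of the last change and the samples.** If the Week 3 change is made at the HD1 visit, as 6.14 reads, all five later samples follow it. If it lags to HD2 or HD3, as 6.13 allows in Week 1, W3-HD2 and possibly W3-HD3 precede it. The three Week 4 samples follow it either way.

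**Step 5. Can a patient frequency be given?** Only under inputs the documents do not supply. Assume six equally correlated normal values per patient, K = m + 0.6 × [√r × b + √(1 - r) × e], with b (shared by a patient's six values) and e (separate for each value) independent standard normal, m = 5.0 or 5.2 mEq/L, SD 0.6 and r = 0.4 or 0.6. No drug effect of a dose change is included. By simulation:

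- At least one of the last five values below 4.0: 17.3% (m = 5.0, r = 0.4), 14.6% (5.0, 0.6), 9.0% (5.2, 0.4), 7.7% (5.2, 0.6). The range is about 8%-17% of the arm.
- Of those patients, 36%-61% had W3-HD1 below 4.5, so 6.7 had already reduced or stopped their drug.
- Leaving out only those already below 4.0 at W3-HD1: 6%-15% of the arm.
- Raised at W3-HD1 (5.5 or more) and later below 4.0: 0.1%-0.8% of the arm, or 0.001 × 20 = 0.02 to 0.008 × 20 = 0.16 patients. If the increase is assumed to lower potassium by a further 0.4 mEq/L, this becomes 1.1%-3.7%, still under one patient in 20.
- At the footnote 3 stop level of 3.5 in place of 4.0: 0.9%-2.7% of the arm with at least one of the five below it.

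The result changes by more than an order of magnitude with the group and threshold chosen.

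**The case against.** **The text is contradictory, so five of six is only one reading.** This stands. The threshold sentence in 6.7 has no visit limit of its own, the heading names Week 4, and neither 3.4 nor footnote 3 is limited to HD1. A reader could combine these to cover all six results. No single passage says so, however: 6.13 and 6.14 attach the rule to particular visits, and 6.14 gives Week 4 no dose step. Each reading in the table leaves at least three results uncovered.

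**The gap might be read as no action of any kind.** That is too broad. Section 6.15 items 2 and 3 both apply in these weeks, and the trial is open label, so staff seeing a low value know who is on drug. What is missing is a stated low-potassium criterion and a named reviewer.

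**A reader might infer that two or three of 20 patients would run low at their highest dose.** The documents do not support this. The 8%-17% covers the whole patiromer arm under assumed inputs, and many of those patients would already have been reduced or stopped. Patients raised at HD1 of Week 3 are those with high values, and few of them fall below 4.0 later under the same assumptions.

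**The cited risk evidence is indirect.** This also stands. The 5.6% is for K below 3.5 over 52 weeks, and section 3.1 also reports the lowest mortality between 4 and 5.5 mEq/L. The point rests on the protocol's own stop criterion.

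**A fixed-dose assessment period after titration is ordinary.** True for dose increases. It does not explain why a stop criterion lapses on the same day, and the protocol gives no reason.

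**Conclusion.** The point holds as a gap and a conflict in a safety rule, and should be fixed. Under 6.7 and 6.14 five of the six Week 3-4 results have no stated low-potassium action; the count is four or three if the Schedule's fourth mark or section 3.4 governs. Followed as written, the rule would let a patient whose value meets the protocol's own stop criterion stay on drug unless the Investigator intervenes under 6.15 item 2, which sets no potassium threshold.

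The size is this count of results over about 11 days. It rests on the six samples in 8.1 and, for the four-of-six reading, on the assumed position of the Schedule mark. No patient frequency should be quoted. It is also not established that all five results follow the last dose increase; only the Week 4 results do so whatever the lag. The sample-size calculation is unaffected.

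**What to change.** Reconcile section 3.4, the heading and text of 6.7, sections 6.13 and 6.14, and the Schedule with footnote 3, so that they agree on:

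- to which on-treatment potassium results the low-potassium criteria apply, naming HD2 and HD3 of Week 3 and all of Week 4;
- who reviews each of those results;
- one set of thresholds, since 6.7 and footnote 3 differ.

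State the stop criterion separately from the titration visits. If the sponsor intends no action on some of these results, say so and give the safety reason. Record any dose change or stop in Weeks 3-4 so that it can be reported with the primary endpoint. The thresholds and actions are for the sponsor and investigator to settle.

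The cost is protocol wording and timely review of results the trial already obtains. The drawback is that a few patients may change dose or stop drug inside the efficacy window.
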